9.2.2 Assessment of Adverse Events

Investigators will assess the occurrence of AEs and SAEs at all subject evaluation time points during the study. All AEs and SAEs, whether volunteered by the subject, discovered by study staff during questioning, or detected through PE, clinically significant laboratory test, or other means, will be recorded in the subject’s medical record and on the AE eCRF and, when applicable, on an SAE form.

Each recorded AE or SAE will be described by its duration (eg, start and end dates), severity, regulatory seriousness criteria, if applicable, suspected relationship to the investigational product (see guidance above), and any actions taken.

All deaths should be reported with the primary cause of death as the AE term, as death is typically the outcome of the event, not the event itself. The primary cause of death on the autopsy report should be the term reported. Autopsy and postmortem reports must be forwarded to Rigel, or designee, as described below.

If study drug is discontinued because of an SAE, this information must be included in the SAE report.

9.2.3 Expedited Reporting Requirements for Serious Adverse Events

An Investigator should report a SAE within 1 day (ie, immediately but no later than the end of the next business day) of his/her awareness of the event by completing and sending the provided SAE form to Rigel's authorized safety representative. [NOTE: In UK, SAEs must be reported within 24 hours.]

Additionally, all fatal or life-threatening SAEs should be telephoned to Rigel as soon as the Investigator learns of the event.

The SAE form should be sent to the following fax or email:

Email: [contact]

Fax: see Study Reference Manual

The site may contact the Medical Monitor (listed below) with questions regarding the reporting of SAEs.

[name]
Medical Monitor
Rigel Pharmaceuticals, Inc.
[contact]
[contact]
[contact]
E-Mail: [contact]

9.2.4 Reporting of Serious Adverse Events by Sponsor

Regulatory Authorities, IECs/IRBs, and Principal Investigators will be notified of SAEs in accordance with applicable requirements (eg, GCPs, ICH guidelines, national regulations, and local requirements). The country-specific requirements, timelines, and processes for complying with these requirements are described in detail in the Study Operations Manual and/or Safety Plan.

Rigel's Safety Surveillance Committee will review and evaluate accumulating safety data from the entire clinical trial database for the study drug at appropriate intervals (eg, quarterly) to identify new safety signals or increased frequency of events. This will include an aggregate review and comparison to the control group of SAEs that were deemed as "not suspected" as being associated with use of the study drug.

9.3 Pregnancy

Although pregnancy itself is not regarded as an AE, the outcome of any pregnancy that occurs during the study must be documented.

Prior to study enrollment, females of childbearing potential must agree in the ICF to take appropriate measures to avoid pregnancy at all times during the study, commencing from the

time of consent to 30 days after the last dose of study drug, and, if pregnancy occurs, they must agree to report the pregnancy and cooperate with the Investigator as set forth below.

Should a pregnancy occur, the female study participant must immediately inform the Investigator and must immediately discontinue study drug. The Investigator should counsel the study participant on any risks of continuing the pregnancy and any possible effects on the fetus in view of the subject's participation in the study. The study participant must agree to follow-up by the Investigator regarding the outcome of any pregnancy that occurs during the study. Outcome is defined as elective termination of the pregnancy, miscarriage, or delivery of the fetus. For pregnancies with an outcome of live birth, the newborn infant will be followed by the Investigator until it is 30 days old. Any congenital anomaly/birth defect noted in the infant must be reported as an SAE.

The Investigator will notify Rigel or its authorized representative of a pregnancy occurring in a female study participant within 14 days of first becoming aware of such pregnancy using the pregnancy notification form. All follow-up information gathered by the Investigator shall be reported to the Sponsor within 14 days of Investigator's first knowledge of such information using the pregnancy exposure form.

10.0 STATISTICAL METHODS

10.1 General Considerations

The statistical analysis of the data obtained from this study will be performed using SAS[®] version 9.2 or higher. All inferential tests will be 2-sided and will be performed using a type I error rate of 5%, unless otherwise indicated.

A detailed statistical analysis plan will be developed as a separate document and will be finalized prior to database lock.

10.2 Analysis Populations

The Intent-to-Treat (ITT) population will include all randomised subjects. All efficacy endpoints will be analyzed based on the ITT population, and subjects will be analyzed according to their randomised treatment assignment. The efficacy analyses based on the ITT population will be considered the primary efficacy analyses.

The Per-Protocol (PP) population will include all subjects in the ITT population who had no major protocol violations. Major protocol violations will include:

- Not receiving any study treatment
- Not receiving the correct study treatment
- Not receiving sufficient treatment
- Failing to meet eligibility criteria
- Other major protocol violations, as determined by a blinded review of the data prior to database lock

For analysis of the primary efficacy endpoint, the main analysis will be performed with baseline defined as the average between Visit 2 and the most recent screening value prior to Visit 2 (a secondary analysis, with the Visit 2 value alone as baseline, will be performed). For all other analyses, baseline measurements will be the last measurement for the corresponding variable prior to the first randomised dose at Visit 2.

Safety and efficacy data from the extended treatment period will not be subjected to statistical analysis.

10.3 Analysis of Efficacy Endpoints

The number of subjects who were screened, enrolled into the study and completed the study through Visit 9 will be summarized by treatment group using all enrolled subjects. The reasons that treated subjects withdrew from the study will also be summarized. Efficacy data from the extended treatment period will not be included in the statistical analysis.

Subject demographic data (age, gender, race, ethnicity) will be summarized by treatment group using the Safety population, as will baseline characteristics of height and weight.

10.3.1 Primary Efficacy Endpoint

The primary efficacy endpoint is the mean change from Baseline (Visit 2) of proteinuria as measured by sPCR at 24 weeks (Visit 9). This will be analyzed using an ANCOVA model in the ITT population. The ANCOVA model will include both the treatment group and the presence/absence of endothelial hypercellularity at baseline as factors and will adjust for the proteinuria at baseline (as a covariate). The urine protein-creatinine ratio will be log-transformed prior to analysis. Missing Week 24 (Visit 9) data will be imputed using a multiple imputation procedure to be described in the SAP.

10.3.2 Secondary Efficacy Endpoints

The safety population will include all randomised subjects who received at least 1 dose of the allocated study drug. The safety population will be analyzed for all safety assessments. The subjects will be analyzed as treated.

Secondary efficacy endpoints related to proteinuria will be measured by sPCR (as is the case for the primary efficacy endpoint).

All secondary efficacy endpoints will be analyzed using both the ITT and PP populations. Additionally, the primary efficacy endpoint will be analyzed using the PP population as a sensitivity analysis. No adjustments will be made for multiplicity.

The following secondary endpoints will be analyzed using an ANCOVA model which includes the treatment group and presence/absence of endothelial hypercellularity at baseline as factors, with mean estimates of the variable adjusted for the baseline value:

- Mean change from pre-treatment to post-treatment in mesangial hypercellularity on renal biopsies.
- Mean change from pre-treatment to post-treatment in endocapillary hypercellularity on renal biopsies.
- Mean change from pre-treatment to post-treatment in segmental sclerosis/adhesion on renal biopsies.
- Mean change from pre-treatment to post-treatment in global glomerulosclerosis score on renal biopsies
- Mean change from pre-treatment to post-treatment in tubulointerstitial scarring on renal biopsies.
- Mean change from Baseline (Visit 2) of eGFR at 12 weeks (Visit 7).
- Mean change from Baseline (Visit 2) of eGFR at 24 weeks (Visit 9).
- Mean change from Baseline (Visit 2) of proteinuria at 12 weeks (Visit 7).
- Shift in haematuria (dipstick test) from Baseline (Visit 2) at 12 weeks (Visit 7).

- Shift in haematuria (dipstick test) from Baseline (Visit 2) at 24 weeks (Visit 9).

Estimates will be provided for the following contrasts: 1) combined fostamatinib group vs. placebo; 2); 150 mg fostamatinib group vs. placebo; and 3) 100 mg fostamatinib group vs. placebo.

Fisher's exact test will be used to assess whether the percentage of subjects who meet the following criteria differ between the pooled fostamatinib and placebo groups:

- Have a $\geq 30\%$ reduction in sPCR from Baseline (Visit 2) to Week 24 (Visit 9)
- Have sPCR $< 50\text{mg}/\text{mmoL}$ at Week 12

The 95% CIs for the percentages will also be provided.

Shift tables will display the change in category from Baseline (Visit 2) to Week 24 (Visit 9) for the following categorical parameters:

- Presence/absence of segmental sclerosis/adhesion
- Presence/absence of global glomerulosclerosis
- Presence/absence of tubulointerstitial scarring

Fisher's exact test will assess whether there is an association between the change in these categories from Baseline (Visit 2) to Week 24 (Visit 9) and treatment group (ie, combined fostamatinib group vs. placebo).

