10.7 Determination of Sample Size

A sample size of 25 evaluable subjects in each of the 3 treatment groups will have an 80% power to detect a 43% reduction in proteinuria from Baseline (Visit 2) to 24 weeks (Visit 9) between the pooled fostamatinib and placebo groups, using a 2-sided t-test with $\alpha = 0.05$ and log-transformed data. This calculation assumes that the 3 treatment groups have the same mean and standard deviations of urinary protein/ creatinine ratio (130 mg/mmol \pm 120 mg/mmol) at Baseline (Visit 2) and that the values for the placebo group remain constant over 24 weeks. Treatment allocation ratio will be 1:2 for the placebo: combined fostamatinib groups.

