3.2 Determination of Sample Size

A sample size of 25 evaluable subjects in each of the 3 treatment groups will have an 80% power to detect a 43% reduction in sPCR from Baseline to Week 24 between the pooled fostamatinib and placebo groups, using a 2-sided t-test with $\alpha = 0.05$ and log-transformed data. This calculation assumes that the 3 treatment groups have the same mean and standard deviations of urinary protein/creatinine ratio and coefficient of variation of 0.923 at Baseline and that the values for the placebo group remain constant over 24 weeks. Treatment allocation ratio will be 1:2 for the placebo: combined fostamatinib groups

Table 1 Study Treatment

Treatment Group	Number of Subjects	Dose
C	25	Placebo bid
A	25	Fostamatinib 100 mg bid
B	25	Fostamatinib 150 mg bid

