5.6 Adjustments for Covariates

The randomization stratification factors and the baseline values of the response variables will be included in the statistical analysis model as covariates.

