7.5 Analysis of Secondary Efficacy Endpoints

All secondary efficacy endpoints will be analyzed using the ITT population except for biopsy endpoints that will be analyzed using the Biopsy Population.

Continuous secondary endpoints will be analyzed using an ANCOVA model which includes the treatment and presence/absence of endothelial hypercellularity at baseline as factors and adjusted

for the baseline value. The LS mean differences between treatment groups (combined fostamatinib group vs placebo; 150 mg fostamatinib group vs placebo; 100 mg fostamatinib group vs placebo separately) accompanied by 95% confidence interval and the p-value for testing the treatment difference will be presented.

Shift tables will display the change in category from pre-study renal biopsy to post-treatment renal biopsy for each of the components of the Oxford Classification scoring:

- Mesangial hypercellularity (M_0 is $\leq 50\%$ of glomeruli show mesangial hypercellularity; M_1 is $> 50\%$ of glomeruli showing mesangial hypercellularity)
- Endocapillary hypocellularity (E_0 is no endocapillary hypercellularity; E_1 is any glomeruli showing endocapillary hypercellularity)
- Segmental glomerulosclerosis (S_0 = absent; S_1 present in any glomeruli)
- Tubular atrophy/interstitial fibrosis (T_0 is 0 – 25% of cortical area shows tubular atrophy or interstitial fibrosis; T_1 is 26 – 50%; T_2 is $> 50\%$)

Cochran–Mantel–Haenszel (CMH) test will assess whether there is an association between the change in these categories from pre-treatment to post-treatment and treatment group (combined fostamatinib group vs placebo; 150 mg fostamatinib group vs placebo; 100 mg fostamatinib group vs placebo separately) while controlling for the presence/absence of endothelial hypercellularity at baseline.

Missing data for the secondary endpoints will not be imputed.

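### SAP 7.5 names no test for the three sPCR responder endpoints; the protocol's unstratified Fisher test covers only two, and stratified CMH would be a small free improvement

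*Protocol*

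**What the plan says.** Both documents list three sPCR responder endpoints as secondary (Protocol 4.3, SAP 4.3): at least 30% reduction at Week 24, at least 50% reduction at Week 24, and sPCR below a threshold at Week 12.

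- **Protocol 10.3.2:** "Fisher's exact test will be used to assess whether the percentage of subjects who meet the following criteria differ" between pooled fostamatinib and placebo. The criteria listed are the 30% reduction and the Week 12 threshold. The 50% reduction is not in the list. Confidence intervals are promised for the percentages, not for a difference.
- **SAP 7.5:** ANCOVA for continuous secondary endpoints. For the Oxford M, E, S and T shift categories it plans a CMH test "while controlling for the presence/absence of endothelial hypercellularity at baseline", for three contrasts. It names no method for responder percentages.
- **SAP 5.5:** estimates of three contrasts for efficacy endpoints (combined, 150 mg and 100 mg, each against placebo).
- **SAP 5.6:** "The randomization stratification factors and the baseline values of the response variables will be included in the statistical analysis model as covariates".
- **SAP 3.3 and Protocol 5.3.1:** randomisation is stratified by presence or absence of endocapillary hypercellularity.

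**The concern.** The one test written down for responders takes no account of the randomisation stratum, covers one contrast of three and two endpoints of three, and is known to be conservative in small samples. The SAP, which should settle the analysis, does not mention it.

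The protocol also specified Fisher's test for its biopsy categories, and the SAP replaced that with a stratified CMH test. The responder endpoints did not receive the same update.

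Two things are at stake. One is a few points of power on secondary endpoints. The other is that Fisher, CMH or logistic regression could each be chosen after unblinding. No multiplicity adjustment is planned (SAP 5.8), and SAP section 8 has Cohort 1 unblinded for the interim analysis, so the choice is better fixed in advance.

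**Working it through.** **1. The plan's own figure.** The only stated power is for the primary endpoint: "80% power to detect a 43% reduction in sPCR from Baseline to Week 24 between the pooled fostamatinib and placebo groups". The inputs are a baseline of "130 mg/mmol \pm 120 mg/mmol" (120/130 = 0.923, matching the SAP's "coefficient of variation of 0.923 at Baseline"), two-sided 5%, and 25 placebo versus 50 pooled fostamatinib.

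- SD of ln sPCR = √ln(1 + 0.923²) = 0.785
- Difference = −ln(0.57) = 0.562
- Standard error = 0.785 × √(1/25 + 1/50) = 0.192
- 0.562/0.192 = 2.92, which gives power of 82.2% (noncentral t, 73 df)

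The stated 80% is reproduced and slightly conservative. No power or size is given for any responder endpoint.

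**2. True size of the two tests.** The group sizes of 50 and 25 follow from "A sample size of 25 evaluable subjects in each of the 3 treatment groups". Fisher's size is the sum, over all pairs of responder counts (x of 50, y of 25) with Fisher p ≤ 0.05, of the product of two binomial probabilities at a common rate p.

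For CMH, assume an even stratum split of 25/12 and 25/13 (active/placebo). In stratum k let a be active responders, t all responders, n and m the active and placebo numbers, and N = n + m. Then d = a − nt/N and v = nmt(N − t)/[N²(N − 1)]. Reject when (Σd)²/Σv ≥ 3.84. Enumerating all tables gives:

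| Common rate | Fisher | Stratified CMH |
|---|---|---|
| 10% | 3.0% | 4.0% |
| 20% | 3.3% | 5.1% |
| 30% | 3.5% | 4.9% |
| 40% | 4.0% | 5.0% |

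Simulation gave 3.9% for CMH at the 10% rate, so CMH is itself conservative there. For the single-dose contrasts (25 versus 25, strata of 12 and 13 per arm), the same enumeration puts CMH at 4.9% to 5.4% for rates of 10% to 50%. Fisher there would be 0.9% to 3.3%, although the protocol does not plan it for those contrasts.

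**3. Power.** The rates and stratum effects below are assumptions; the documents give none.

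- *50% versus 20%, no stratum effect:* Fisher 71.2%, CMH 73.7%, a gap of 2.5 points.
- *Stratum log-odds of ±0.5:* the rates become 62.2% and 37.8% on active, and 29.2% and 13.2% on placebo. With the higher-response stratum holding 12 placebo subjects, Fisher has 68.4% and CMH 71.9%, a gap of 3.5 points. Of these, 2.5 are present with no stratum effect at all.
- *The same with 13 placebo subjects in the higher-response stratum:* Fisher 66.0%, CMH 71.9%, a gap of 5.9 points. The strata then account for the larger part.
- *Rates implied by the design for a 30% reduction*, taking the SD of log change as 0.785: placebo Φ(ln 0.7/0.785) = 32.5%; active Φ((ln 0.7 + 0.562)/0.785) = 60.3%. Fisher has 60.1% and a one-stratum CMH 63.1%.

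**4. Adding baseline.** A separate simulation used 2,000 trials per scenario. It assumed a baseline to follow-up correlation of 0.5 to 0.8, 40% with endocapillary hypercellularity, and a stratum effect of 0 or 0.4 log units. Stratifying alone gained about 1 to 6 points over Fisher. Logistic regression with stratum and log baseline sPCR gained about 2 to 14 points for the 30% reduction and 13 to 31 for the Week 12 threshold. Its likelihood-ratio test had a size of 5.2% to 7.0%, so part of that gain is inflated.

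**The case against.** Fisher's test is valid, pre-specified in the protocol for two endpoints, and keeps type I error below 5%. Conservatism in small samples is a known property and buys guaranteed size in sparse tables. The responder endpoints are secondary and unpowered in a Phase 2 proof-of-concept trial, and the primary ANCOVA already adjusts for stratum and baseline. All of this stands, and it limits the point to a minor one.

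A reader might infer that the SAP contradicts its own section 5.6. The documents do not support that. Section 5.6 concerns covariates in a statistical model, Fisher's test appears only in the protocol, and the SAP does not carry it forward. The SAP is silent on the responder method, and 5.6 could even be read as covering it.

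A reader might also infer that power is lost mainly because the strata are ignored. With no stratum effect, 2.5 points of gap remain, which is Fisher's discreteness. Only in the less favourable of the two stratum layouts in step 3 do the strata account for more than half.

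What the objection does not answer is that the SAP names no responder test and that the 50% responder has none in either document.

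**Conclusion.** The specification gap is real: two responder endpoints have a test in the protocol that the SAP drops without comment, and the third has no named test anywhere. Fisher's test is not wrong. Replacing it with CMH stratified by the randomisation factor would bring the size closer to 5% and gain about 2.5 to 3.5 points of power at 50% versus 20% (up to about 6 in the less favourable stratum layout).

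These power figures rest on assumed response rates, an even stratum split and complete data. The size figures rest on 50 versus 25 evaluable subjects. The primary analysis and the stated sample size are unaffected. This is a free improvement of low severity.

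**What to change.** In SAP 7.5, add that each of the three responder endpoints (30% and 50% reduction at Week 24, and the Week 12 threshold) will be compared by a CMH test stratified by the randomisation factor. Apply it to the three contrasts in SAP 5.5, and report a stratified risk difference with 95% CI. Record that this replaces the protocol's Fisher test. Call the stratum endocapillary hypercellularity, as in the randomisation section, because SAP 7.5 currently says endothelial.

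Logistic regression with stratum and log baseline sPCR could be supportive, but only with a small-sample method, given the 5.2% to 7.0% size of the likelihood-ratio test.

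Two related items belong in the same edit. State how subjects with missing sPCR count in the percentages, since secondary data are not imputed. Reconcile the Week 12 threshold, which is 50 mg/mmol (442 mg/g) in the protocol and 500 mg/g (56.6 mg/mmol) in the SAP.

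The cost is a few SAP sentences. Stratified CMH is already specified for the biopsy shifts, and no new data are needed.

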10.4 Analysis of Safety

All safety variables will be analyzed using the Safety population. The safety population will include all randomised subjects who received at least 1 dose of the allocated study drug. The safety population will be used for analysis of all safety assessments through Visit 10. Safety data from the extended treatment period will not be included in the statistical analysis.

The safety endpoints will assess the safety and tolerability of fostamatinib as assessed by the incidence of adverse events, clinical laboratory results (haematology, serum chemistry, and urinalysis), vital signs, and physical examinations. Safety parameters of particular interest will include increases in blood pressure, adverse effects on liver function tests including transaminase elevations, diarrhoea, other GI symptoms and neutropenia.

The safety outcomes of this study include the change from baseline in blood pressure, liver function, and absolute neutrophil count (ANC) and the incidence of GI complaints and infections, as well as the incidence of any adverse events.

For each treatment group, descriptive statistics will be presented by visit for the actual values and the changes from baseline for systolic and diastolic blood pressure, each liver function test (ALT, AST, alkaline phosphatase, and bilirubin [total, direct, and indirect]), and ANC.

The difference between fostamatinib and placebo in the mean change from baseline will also be presented for each endpoint. The numbers and percentages of subjects with GI complaints and infections at any time during the double-blind treatment period will be presented by treatment group for the Safety Population. Fisher's Exact Test will be used to test for a difference between fostamatinib and placebo in the proportions of subjects experiencing GI complaints and infections.

AEs will be coded using the Medical Dictionary for Regulatory Activities (MedDRA). The number and percentage of subjects with at least 1 adverse event, at least 1 serious adverse event (SAE), and at least 1 treatment related adverse event will be presented by treatment group. AEs that are possibly or probably related to study treatment, or for which the relationship to study treatment is missing, will be considered treatment related. AEs will be summarized at the subject level by MedDRA system organ class (SOC) and preferred term using frequencies and percentages. AEs will also be tabulated at the event level by severity and by relationship to study treatment for each treatment group.

